8.15 Biomarker Assessments

Blood samples for future biomarker assessments will be drawn during the clinic visits at Baseline and Weeks 1, 4, 8 and 13. Samples will be drawn at the time of the clinic visit, with documentation of the date and time the samples were obtained.

Blood samples will be collected in Vacutainer tubes (2 x 4 mL) containing K2 EDTA as a preservative. Blood samples will be kept on wet ice from the time of collection and throughout processing until frozen.

One tube will be centrifuged at approximately 3000 rpm for 10 minutes at 4°C. If a chilled centrifuge is not available, it is acceptable to keep sample on wet ice prior to centrifugation and use an ambient centrifuge to process the sample. The resulting plasma sample will be harvested

and transferred evenly into two appropriately labeled polypropylene screw-cap tubes. The other tube will be retained as whole blood. The plasma and whole blood tubes for biomarker use will be placed in a freezer at -70°C within 60 minutes of the blood draw. If a clinical site does not have a -70°C or -80°C freezer, it is acceptable to use a -20°C freezer, but samples stored must be shipped for storage with the laboratory vendor within 2 weeks of collection. These biomarker samples will be retained and may be utilized subsequently for biomarker assessment.

9 EVALUATION AND REPORTING OF ADVERSE EVENTS

9.1 Adverse Events

An adverse event is defined as any untoward medical occurrence in a clinical investigation subject administered a pharmaceutical product, which does not necessarily have a causal relationship with this treatment. An adverse event can therefore be any unfavorable and/or unintended sign (including an abnormal laboratory finding), symptom, or disease temporally associated with the use of an investigational medicinal product, whether or not related to the investigational medicinal product. All adverse events, including observed or volunteered problems, complaints, or symptoms, are to be recorded on the appropriate eCRF.

Adverse events, which include abnormal and clinically significant clinical laboratory test variables, will be monitored and documented from the time Informed Consent until study participation is complete (the Follow-up Visit). Subjects should be instructed to report any adverse event that they experience to the Investigator. Any medical condition present prior to consent should be recorded in medical history. Beginning with the signing of the informed consent until the time of the first dose of study drug, investigators should make updates to source records to document any pre-existing medical condition or signs or symptoms that change in severity, frequency, or seriousness in the medical history; if the subject is subsequently randomized, these occurrences will be reported as adverse events that began prior to dosing. Serious adverse events that occur prior to the first dose of study drug should be reported similarly, except that an SAE report will be completed regardless of whether the subject is randomized.

Beginning with the first dose of study drug, investigators should make an assessment for adverse events at each visit and record all adverse events, non-serious and serious, on the appropriate adverse event eCRF.

Wherever possible, a specific disease or syndrome rather than individual associated signs and symptoms should be identified by the Investigator and recorded on the eCRF. However, if an observed or reported sign or symptom is not considered a component of a specific disease or syndrome by the Investigator, it should be recorded as a separate adverse event on the eCRF. Additionally, the condition that led to a medical or surgical procedure (e.g., surgery, endoscopy, tooth extraction, or transfusion) should be recorded as an adverse event, not the procedure. Concomitant procedures should be recorded as such on the appropriate eCRF.

Clinically significant abnormal laboratory values or other examinations (e.g., ECG) that are detected after the first dose of study drug and worsen during the study should be reported as adverse events. An abnormal laboratory result that is not verified by repeat testing does not necessitate reporting as an adverse event. The Investigator will exercise his or her medical,

scientific, and clinical judgment in deciding whether an abnormal laboratory finding or other abnormal assessment is clinically significant. Clinically significant abnormal laboratory values occurring during the clinical study will be followed until repeat tests return to normal, stabilize, or are no longer clinically significant. Any abnormal test that is determined to be an error does not require reporting as an adverse event.

Treatment of any adverse reactions will be evaluated and managed by a physician.

9.2 Definitions

9.2.1 Adverse Drug Reaction

For adverse events with a causal relationship to study drug, follow-up by the Investigator will be required until the event or its sequelae resolve or stabilize to a level acceptable to the Investigator.

9.2.2 Unexpected Adverse Event/ Unexpected Adverse Drug Reaction

An unexpected AE/unexpected suspected adverse reaction is an AE or suspected adverse reaction that is not listed in the Investigator Brochure or is not listed at the specificity or severity that has been observed; or, if an Investigator Brochure is not required or available, is not consistent with the risk information described in the general investigational plan or elsewhere in the current application, as amended.

9.2.3 Serious Adverse Events

An adverse event or adverse reaction is considered serious if, in the view of either the Investigator or Sponsor, it results in any of the following outcomes:

- Death;
- A life-threatening adverse event;
- NOTE: An adverse event or adverse reaction is considered “life-threatening” if, in view of either the Investigator or Sponsor, its occurrence places the subject at immediate risk of death. It does not include an event that, had it occurred in a more severe form, might have caused death.
- Requires hospitalization or prolongation of existing hospitalizations;
NOTE: Any hospital admission with at least one overnight stay will be considered an inpatient hospitalization. An emergency room visit without hospital admission will not be recorded as a SAE under this criterion, nor will hospitalization for a procedure scheduled or planned before signing of informed consent. However, unexpected complications and/or prolongation of hospitalization that occur during elective surgery should be recorded as adverse events and assessed for seriousness. Admission to the hospital for social or situational reasons (i.e., no place to stay, live too far away to come for hospital visits) will not be considered inpatient hospitalizations.
- A persistent or significant disability/incapacity or substantial disruption of the ability to conduct normal life functions;
- A congenital anomaly/birth defect; or
- An important medical event.
NOTE: Important medical events that may not result in death, be life-threatening, or require hospitalization may be considered an SAE when, based upon appropriate medical

judgment, they may jeopardize the subject and may require medical or surgical intervention to prevent one of the outcomes listed in this definition. Examples of such medical events include allergic bronchospasm requiring intensive treatment in an emergency room or at home, blood dyscrasias or convulsions that do not result in inpatient hospitalizations, or the development of drug dependency or drug abuse.

9.3 Assessment of Adverse Events by the Investigator

9.3.1 Causality/Relatedness

The relationship of an adverse event to the administration of the study drug is to be assessed by the Investigator according to the following definitions:

Not Related (unlikely related, unrelated, not related, no relation) – The time course between the administration of study drug and the occurrence or worsening of the adverse event rules out a causal relationship and/or another cause (e.g., medical history, concomitant drugs, therapies, and complications) is suspected.

Related (possibly related, related) – The time course between the administration of study drug and the occurrence or worsening of the adverse event is consistent with a causal relationship and no other cause (e.g., medical history, concomitant drugs, therapies, and complications) can be identified.

The definition implies a reasonable possibility of a causal relationship between the event and the study drug. This means that there are facts (evidence) or arguments to suggest a causal relationship. The following factors should also be considered:

- The temporal sequence from study drug administration - The event should occur after the study drug is given. The length of time from study drug exposure to event should be evaluated in the clinical context of the event.
- Underlying, concomitant diseases (medical history) - Each report should be evaluated in the context of the natural history and course of the disease being treated and any other disease the subject may have.
- Concomitant drug - The other drugs the subject is taking or the treatment the subject receives should be examined to determine whether any of them might be recognized to cause the event in question.
- Known response pattern for this class of study drug - Clinical and/or preclinical data may indicate whether a particular response is likely to be a class effect.
- Exposure to physical and/or mental stresses - The exposure to stress might induce adverse changes in the recipient and provide a logical and better explanation for the event.

- The pharmacology and PK of the study drug - The known pharmacologic properties (absorption, distribution, metabolism, and excretion) of the study drug should be considered.

9.3.2 Severity

The Investigator is responsible for assessing the severity (intensity) of each adverse event as mild, moderate, or severe according to the following definitions:

Mild – An event that is easily tolerated and generally not interfering with normal daily activities.

Moderate – An event that is sufficiently discomforting to interfere with normal daily activities.

Severe – An event that is incapacitating with inability to work or perform normal daily activities.

It should be noted that a severe AE need not be serious and that a serious adverse event (SAE) need not, by definition, be severe.

9.3.3 Adverse Event Monitoring and Follow-up

Subjects who experience AEs will be monitored with relevant clinical assessments and laboratory tests, as determined by the Investigator. In accordance with good medical practice, all AEs must be followed to satisfactory resolution or stabilization of the event(s), or, if a chronic condition, until fully characterized. All follow-up results are to be reported to the Sponsor. Any actions taken and follow-up results must be recorded either on the appropriate page of the CRF or in a follow-up letter to the Sponsor, as well as in the subject's source documentation. Follow-up laboratory results should be filed with the subject's source documentation.

For all AEs that require the subject to be discontinued from the study, relevant clinical assessments and laboratory tests must be repeated at appropriate intervals until final resolution or stabilization of the event(s).

Subjects who have non-serious AEs that are ongoing at study completion or study withdrawal must be followed until resolution of the AEs or for 30 days after the last dose of study drug, whichever comes first. Subjects who have an ongoing SAE at study completion or study withdrawal must be followed until the event resolves or the event or sequela stabilizes.

9.3.4 Reporting Serious Adverse Events

From the time of informed consent until 30 days following the last administration of study drug The Investigator or designee will notify the sponsor contact and clinical research organization (CRO) within 24 hours after the SAE detection, observation, or report of occurrence (regardless of the relationship to study treatment). The Sponsor and the CRO medical monitor contact information for SAE reporting is provided below.

[REDACTED]
Tetra Discovery Partners, Inc.
Email: [REDACTED]
Office: [REDACTED]
24-hour contact number (cell): [REDACTED]

and

[REDACTED]
[REDACTED]
Syneos Health

Email: [REDACTED]

24-hour contact number (cell): [REDACTED]

The final SAE report must contain the following information, but the event may be initially reported without complete data, if necessary:

Study name/number

Study drug

Investigator details (name, phone, fax, e-mail)

Subject number (randomization number)

Subject initials

Subject demographics (age, date of birth, sex, weight)

Clinical event

- Description
- Date of onset
- Treatment (drug, dose, dosage form)
- AE relationship to study drug
- Action taken regarding study drug in direct relationship to the AE

If the AE was fatal or life-threatening

Cause of death (whether or not the death was related to study drug)

Autopsy findings (if available)

The Investigator must continue to follow the subject until the SAE has subsided or until the condition becomes chronic in nature, stabilizes (in the case of persistent impairment), or the subject dies. Within 24 hours of receipt of follow-up information, the Investigator must update the Sponsor and submit any supporting documentation (e.g., subject discharge summary or autopsy reports).

Any new SAE that occurs within one month after the study period and is considered to be possibly related to the investigational product should be recorded and reported immediately to the Sponsor.

All serious event reporting will adhere to Code of Federal Regulations (CFR), specifically 21 CFR 312.32 (7- and 15-day alerts) for Investigational New Drugs (IND). The clinical research site will be responsible for reporting SAEs to the Institutional Review Board (IRB) per FDA regulations. The Sponsor will be responsible for reporting and processing any SAEs to the FDA or other applicable regulatory agency.

9.4 Data Safety and Monitoring Committee

An independent data and safety monitoring board (DSMB) will provide safety oversight for this study. The DSMB will consist of two qualified MDs and one statistician. The DSMB will review standard safety data approximately every four (4) months, based on enrollment rate. A

DSMB charter will be developed to further outline the DSMB responsibilities and the desired listings, summaries and analyses.

9.5 Reports of Pregnancy

If a subject or partner of a subject participating in the study becomes pregnant during the study or within 30 days of discontinuing study drug, the Investigator should report the pregnancy to the Sponsor within 24 hours of being notified. Investigator will complete then forward the Exposure In Utero form to the Sponsor.

A subject becoming pregnant while on study drug will immediately be withdrawn from the study and early termination study procedures will be performed.

The subject should be followed by the Investigator until completion of the pregnancy. If the pregnancy ends for any reason before the anticipated date, the Investigator should notify the Sponsor. At the completion of the pregnancy, the Investigator will document the outcome of the pregnancy. If the outcome of the pregnancy meets the criteria for immediate classification as an SAE (i.e., postpartum complication, spontaneous abortion, stillbirth, neonatal death, or congenital anomaly), the Investigator should follow the procedures for reporting an SAE.

10 STUDY PROCEDURES AND ASSESSMENTS BY VISIT

10.1 Schedule of Assessments

The study timetable in the Schedule of Assessments shows the schedule of planned study procedures. Every effort should be made to adhere to this procedure schedule.

10.2 Screening (Day -28 to Day -1)

The study will consist of a Screening period of 28 days or less, unless additional time is required for washout of concomitant medications.

Each potential study participant will have the following assessments completed by the Investigator or designee up to 28 days prior to the first dose of study medication:

- Obtain informed consent;
- Obtain medical/surgical history;
- Obtain demographics and social history (tobacco, alcohol, and/or drug use);
- Obtain prior/concomitant medication use;
- Obtain vital signs;
- Obtain height and weight;
- Conduct full physical exam;
- Conduct single ECG;
- Serology (HbsAg, HCV)
- Serum pregnancy (females of childbearing potential , even if using birth control)
- Draw blood samples for Chemistry and Hematology (fasting or nonfasting);
- Collect urine for safety urinalysis;
- ApoE4 testing, if not in medical history;

- Conduct C-SSRS assessment;
- Conduct RBANS, MMSE, CDR and MHIS evaluations
- Evaluate inclusion and exclusion criteria.

10.3 Baseline (Day 1)

Subjects will return to the clinic for the Baseline Visit following successful screening.

Prior to Randomization

The following assessments will be completed:

- Complete urine pregnancy test (females of childbearing potential , even if using birth control)
- Conduct abbreviated physical exam;
- Obtain vital signs;
- Obtain weight;
- Draw blood samples for Chemistry, Hematology and Lipids (following a minimum 8-hour fast);
- Draw blood sample for biomarkers (no PK sample drawn);
- Collect urine for safety urinalysis;
- Conduct ECG (single);
- Conduct C-SSRS assessment;
- Conduct RBANS and MMSE evaluations;
- Conduct ADCS-ADL assessment;
- Record any updates to medical/surgical history;
- Record any updates to prior/concomitant medication use;
- Assess and record and adverse events;
- Re-evaluate inclusion and exclusion criteria based on preceding activities; and
- Verify continued eligibility.

If subject remains eligible for the study:

- Randomize subject;
- Dispense study medication

10.4 Week 1 (Day 7 ± 2)

The following assessments will be completed at the Week 1 visit:

- Collect vital signs;
- Conduct ECG (single);
- Draw blood samples for Chemistry and Hematology (fasting or nonfasting);
- Draw blood samples for pharmacokinetic analysis and biomarkers;
- Collect urine for safety urinalysis;
- Conduct C-SSRS assessment;
- Conduct RBANS, MMSE, and CGI-I evaluations;
- Record pill count remaining in bottle to assess dosing compliance;

- Record any updates to concomitant medication use; and
- Assess and record and adverse events.

10.5 Week 2 (Day 14 ± 2)

The following assessments will be completed at the Week 2 visit:

- Collect vital signs;
- Conduct ECG (single);
- Draw blood samples for Chemistry and Hematology (fasting or nonfasting);
- Conduct RBANS and MMSE evaluations;
- Assess CGI-I;
- Collect study medication and record pill count remaining in bottle to assess dosing compliance;
- Dispense study medication;
- Record any updates to concomitant medication use; and
- Assess and record and adverse events.

10.6 Week 4 (Day 28 ± 2)

The following assessments will be completed at the Week 4 visit:

- Collect vital signs;
- Conduct ECG (single);
- Draw blood samples for Chemistry and Hematology (fasting or nonfasting);
- Draw blood samples for pharmacokinetic analysis and biomarkers;
- Collect urine for safety urinalysis;
- Conduct C-SSRS assessment;
- Conduct RBANS and MMSE evaluations;
- Assess CGI-I;
- Collect study medication and record pill count remaining in bottle to assess dosing compliance;
- Dispense study medication;
- Record any updates to concomitant medication use; and
- Assess and record and adverse events.

10.7 Week 8 (Day 56 ± 3)

The following assessments will be completed at the Week 8 visit:

- Collect vital signs;
- Conduct ECG (single);
- Draw blood samples for Chemistry and Hematology (fasting or nonfasting);
- Draw blood samples for pharmacokinetic analysis and biomarkers;
- Conduct RBANS and MMSE evaluations;
- Conduct ADCS-ADL assessment;

- Assess CGI-I;
- Collect study medication and record pill count remaining in bottle to assess dosing compliance;
- Dispense study medication;
- Record any updates to concomitant medication use; and
- Assess and record and adverse events.

10.8 Week 13 (Day 91 ± 3)

The following assessments will be completed at the Week 13 visit:

- Conduct full physical exam;
- Collect weight;
- Collect vital signs;
- Conduct ECG (single);
- Draw blood samples for:
 - Chemistry, Hematology and Lipids (following a minimum 8-hour fast);
 - Pharmacokinetic analysis and biomarkers;
 - Serum pregnancy test (females of childbearing potential , even if using birth control);
- Collect urine for safety urinalysis;
- Conduct RBANS, MMSE and CDR evaluations;
- Conduct ADCS-ADL assessment;
- Assess CGI-I;
- Conduct C-SSRS assessment;
- Collect study medication and record pill count remaining in bottle to assess dosing compliance;
- Record any updates to concomitant medication use; and
- Assess and record and adverse events.

10.9 Week 14 Follow-up Visit (Day 98 ± 3)

The following assessments will be completed at the final follow up visit at Week 14:

- Obtain vital signs;
- Conduct abbreviated physical exam;
- Assess and record AEs;
- Record any updates to concomitant medication use; and
- Record final subject disposition.

10.10 Early Termination

It is hoped that all subjects can be followed through to the conclusion of the study at Week 14. However, if an early termination occurs, the Week 13 procedures should be completed at the time of the subject's withdrawal (if possible) and an explanation provided as to why the subject

is withdrawing or being withdrawn from the study. Procedures to be completed early termination:

- Conduct a full physical exam;
- Collect weight;
- Collect vital signs;
- Conduct ECG (single);
- Draw blood samples for:
 - Chemistry, Hematology and Lipids (following a minimum 8-hour fast);
 - Pharmacokinetic analysis;
 - Serum pregnancy test (females of childbearing potential, even if using birth control);
- Collect urine for safety urinalysis;
- Conduct RBANS, MMSE, and CDR evaluations;
- Conduct ADCS-ADL assessment;
- Conduct C-SSRS assessment;
- Collect study medication and record pill count remaining in bottle to assess dosing compliance;
- Record any updates to concomitant medication use;
- Assess and record and adverse events; and
- Record final subject disposition.

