Subjects will return to the clinic at the end of Weeks 1, 2, 4, 8, and 13, and for a follow-up safety visit approximately one week after completing the Double-Blind period. Fasting blood samples will be collected at the Week 13 visit. During clinic visits, adverse effects will be assessed, and laboratory measures, vital signs, and ECG will be repeated according to the Schedule of Assessments. Efficacy measures will be obtained to measure the effects of BPN14770 on cognition as well as functional status at Weeks 1, 2, 4, 8, and 13. Every effort will be made to retain each subject throughout the entire study period; however, if a subject must be withdrawn prior to Week 13, all Week 13 safety assessments should be completed, if possible.

Subject Inclusion/Exclusion Criteria:

Individuals are eligible for the study if they meet all of the Inclusion and none of the Exclusion criteria. The criteria below will be assessed during Screening, which will be up to 28 days prior to first study drug administration. Continued subject eligibility will be verified on Baseline Day 1.

Subject Inclusion Criteria

1. Males or females between the ages of 55 and 85 years (inclusive) with a clinical diagnosis of early stage AD, defined according to the following criteria assessed prior to randomization:
 - a) Clinical Dementia Rating (CDR) score of 0.5 or 1, with Memory Box score of 0.5 or greater
 - b) MMSE score of 20 or greater
 - c) RBANS DMI score \leq 85

Note: PET imaging for amyloid is not required for diagnosis, which will be made on clinical grounds.

2. Currently receiving a stable dose regimen of donepezil or another cholinesterase inhibitor for treatment of

Name of Sponsor/Company:	Tetra Discovery Partners, Inc.
Name of Investigational Product:	BPN14770
Study Title:	A Randomized, Double-blind, Placebo-controlled, 3-Arm Parallel Design Study to Evaluate the Effects of BPN14770 in Patients with Early Stage Alzheimer's Disease
Study Number:	BPN14770-CNS-201
Study Phase:	Phase 2

Alzheimer's disease. Subjects must be receiving a stable dose of a cholinesterase inhibitor for at least 56 days prior to their baseline visit. Doses of these drugs may not be changed during the trial.

Note: Memantine is not permitted during the trial and must be discontinued at least 3 weeks prior to Baseline.

3. Modified Hachinski Ischemia score ≤ 4 .
4. Body mass index (BMI) $\leq 38 \text{ kg/m}^2$, inclusive, and body weight of $>48 \text{ kg}$ (105 pounds) at screening.

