6.4 Subject Withdrawal

All subjects have the right to withdraw from this study at any time. In addition, it is the right of the Investigator to remove subjects from the study as a result of adverse reactions, a protocol violation, or non-compliance, or any other reason. Subjects must be discontinued for the following reasons:

- Subject withdraws consent or requests discontinuation from the study for any reason;
- Occurrence of a medical condition or circumstance that exposes the subject to substantial risk and/or does not allow the subject to adhere to the requirements of the protocol as determined by the Investigator;
- Any serious adverse event (SAE), clinical significant adverse event, severe laboratory abnormality, concomitant illness, or other medical condition which indicates to the Investigator that continued participation is not in the best interest of the subject;
- Pregnancy;
- Requirement for prohibited concomitant medication;
- Termination of the study by the Sponsor or the regulatory authority.

Should a subject withdraw after administration of BPN14770 (or placebo), or should the Investigator decide to withdraw the subject, all efforts will be made to complete and report the protocol-stipulated observations up to the time of withdrawal. Week 13 procedures (see Section 10.3 Week 13) and [Section 16.1 Schedule of Study Assessments](#)) will be completed at the time of the subject's withdrawal and an explanation provided as to why the subject is withdrawing or being withdrawn from the study.

In a case of subjects lost to follow-up, attempts to contact the subject must be made and documented in the subject's medical records.

The Investigator must document the primary reason for discontinuation of a study subject on the appropriate case report form (CRF). If the reason for withdrawal is a clinical AE, monitoring will continue until the AE resolves or the Investigator assesses the AE as chronic and stabilized.

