8.11 Additional Safety Measures

Subjects and caregivers will be instructed to inform the study physician and/or research personnel of any AEs that occur at any time during the study.

Procedures will be completed as specified in this protocol unless contraindicated due to a reported AE.

If, in the judgement of the Investigator, additional testing is required to assess an adverse event or otherwise clinically significant event, this testing should be discussed first with the sponsor unless needed urgently.

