16 APPENDICES

16.1 Schedule of Assessments

	Screening	Baseline	Treatment					Follow-Up
	Days -28 thru Day 0	Day 1	Week 1	Week 2	Week 4	Week 8	Week 13 ^e	Week 14
Visit Number	1	2	3	4	5	6	7	8
Target Study Day	---	1	7	14	28	56	91	98
Visit Window			±2	±2	±2	±3	±3	±3
Informed Consent	X							
Eligibility Criteria Confirmed	X	X						
Medical/Surgical History	X	X						
Demographics and Social History	X							
Full Physical Exam	X						X	
Abbreviated Physical Exam		X						X
Height, Weight, BMI	X	X ^a					X ^a	
Vital Signs ^b	X	X	X	X	X	X	X	X
ECGs (single)	X	X	X	X	X	X	X	
Serology (HbsAg, HCV)	X							
Chemistry and Hematology	X	X ^c	X	X	X	X	X ^c	
Lipids		X ^c					X ^c	
ApoE4 testing	X							
Serum Pregnancy ^d	X						X	
Urine Pregnancy ^d		X						
Urinalysis	X	X	X		X		X	
C-SSRS	X	X	X		X		X	
RBANS	X	X	X	X	X	X	X	
MMSE	X	X	X	X	X	X	X	
CGI-I			X	X	X	X	X	
ADCS-ADL		X				X	X	
CDR	X						X	
Hachinski (MHIS-NACC)	X							
PK and Biomarker Sampling		X (biomarkers only)	X		X	X	X	
Randomization		X						
Dispense Medication		X		X	X	X		
First Dose of Medication		X (PM dose following dinner)						
Daily Medication Administration BID			X-----X					
Medication accountability			X	X	X	X	X	
Prior/Concomitant Medication Recording	X	X	X	X	X	X	X	X
Adverse Event Recording		X	X	X	X	X	X	X

Final Disposition									X
-------------------	--	--	--	--	--	--	--	--	---

^a Weight only

^b Vital signs include pulse rate, blood pressure, respiration rate, and temperature

^c Fasting for a minimum of 8 hours prior to blood draw is required at Baseline (Day 1) and End of Treatment (Week 13)

^d All females of childbearing potential, even if using birth control)

^e If a subject terminates from the study prior to Week 13, evaluations intended for Week 13 should be completed at discontinuation, if possible.

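### Subjects who stop early have no scheduled adverse event check after the termination visit, whereas completers have one at Week 14: a small gap that is cheap to close

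*Protocol*

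**What the plan says.** For subjects who leave early, Protocol 10.10 states that "if an early termination occurs, the Week 13 procedures should be completed at the time of the" subject's withdrawal, if possible. The procedures listed there include an AE assessment and end with "Record final subject disposition". No visit or call follows.

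The other places that deal with early withdrawal agree:
- Footnote e in Protocol 16.1, repeated in SAP Table 2: "If a subject terminates from the study prior to Week 13, evaluations intended for Week 13 should be completed at discontinuation, if possible". The Week 14 column is not mentioned.
- Synopsis, Study Procedures: "if a subject must be withdrawn prior to Week 13, all Week 13 safety assessments should be completed, if possible".
- Protocol 6.4: Week 13 procedures at the time of withdrawal, and nothing scheduled later.

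For completers, Protocol 10.9 sets a separate visit at Day 98 ± 3, with vital signs, an abbreviated physical examination, AEs, concomitant medication and final disposition. The synopsis ties this visit to completion of the double-blind period.

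The protocol does follow withdrawn subjects in several ways:
- Protocol 6.4: "If the reason for withdrawal is a clinical AE, monitoring will continue until the AE resolves" or is judged chronic and stable.
- Protocol 9.3.3: non-serious AEs ongoing at withdrawal are followed to resolution or to 30 days after last dose, whichever is first.
- Protocol 9.3.4 and 9.5: serious AEs and pregnancies are covered to 30 days.
- Protocol 8.11: subjects and caregivers are told to "inform the study physician and/or research personnel of any AEs that occur at any time during the study".

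**The concern.** SAP 11.3 counts as treatment-emergent any AE starting on or after first dose and sets no end date. A new event in the week after last dose therefore enters the tables if it is collected. Completers are asked about that week on a schedule. Early terminators are not, unless their termination visit happens to fall some days after their last dose.

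The AE tables would then rest on slightly different ascertainment for the two kinds of subject, and some who stop early may have done so for tolerability. Protocol 11.5 compares each dose with placebo, term by term, using Fisher's exact test, and SAP 3.1 says the outcomes will inform the Phase 3 dose. What is at stake is the completeness and comparability of those AE counts.

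**Working it through.** **Step 1. What is already covered after the last on-treatment visit.**

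| Type of AE | Completer | Early terminator |
|---|---|---|
| Caused the withdrawal | not applicable | monitored (6.4, 9.3.3) |
| Non-serious, ongoing at the last visit | followed to resolution or 30 days after last dose (9.3.3) | same |
| Serious | reported to 30 days after last dose (9.3.4) | same |
| New, non-serious | asked at Week 14 (10.9) | volunteered reports only (8.11) |

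Only the last row differs.

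**Step 2. How many subjects.** The plan gives no figure for this gap. The nearest stated quantity is the allowance for dropouts (Synopsis; Protocol 11.1; SAP 3.2).
- Enrolled 3 × 85 = 255; evaluable 3 × 80 = 240.
- 255 − 240 = 15, and 15/255 = 5.9%.
- With an even split (assumed), 15/3 = 5 per arm.

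This is enrolled minus evaluable, for any cause. It stands in for dosed early terminators and does not count them.

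**Step 3. How much observation time.** The nominal interval from Week 13 to Week 14 is 98 − 91 = 7 days.
- Not covered by a scheduled question: 5 × 7 = 35 person-days per arm.
- Share of post-treatment follow-up: 35/(85 × 7) = 35/595 = 5.9%.
- Share of all scheduled person-days: 35/(85 × 98) = 35/8,330 = 0.4%.

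For a dropout proportion p, the last share is p × 7/98. At an assumed 10% it is 0.7%; at 15%, 1.1%; at 20%, 1.4%.

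**Step 4. Effect on an AE table.** One missed subject changes an arm's incidence for a term by 1/85 = 1.2 percentage points.

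**Step 5. Contacts needed.** 15 on the plan's allowance. If dropout were 10% to 15% (an assumption), 255 × 0.10 = 25.5 and 255 × 0.15 = 38.25, or about 26 to 38.

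**The case against.** Three arguments can be made for leaving the plan alone.

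First, the general wording may already intend follow-up for everyone. Protocol 5.3 describes each subject's duration as including 7 days after last dose, 5.1 places a safety visit a week after treatment ends, and 9.1 runs AE collection to the Follow-up Visit. None of these is expressly limited to completers. That makes the intention arguable, but sites will follow the specific section. It closes the subject out at withdrawal, and footnote e moves Week 13 only. If the sponsor does intend a Week 14 contact for all, 10.10 and the footnote still need to say so.

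Second, existing follow-up covers nearly everything that matters clinically, including the subjects who stop for tolerability. This stands, and it is why the point is minor. Volunteered reporting narrows the gap further, though it depends on memory-impaired subjects and their caregivers raising the event.

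Third, early terminators already lose up to 13 weeks of on-treatment observation, beside which one off-drug week is small. This also stands. A common cut-off for treatment-emergent AEs relative to last dose would make counting more even without new contacts. It would collect nothing about the missing week, however, and could discard events that completers report at Week 14.

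A reader might also infer that the ± 3 day windows at Weeks 13 and 14 contradict the one-week follow-up. They do not: the target days are 7 days apart, as stated, and visit windows are ordinary practice.

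**Conclusion.** The gap exists as the text is written, and it is minor. It is limited to new, non-serious AEs that start after the early termination visit and are not volunteered. On the plan's allowance it involves about 15 subjects and about 0.4% of scheduled person-days, with 1.2 percentage points per missed subject in an arm of 85. These figures assume that enrolled minus evaluable approximates the dosed early terminators, that they split evenly over the arms, and that each loses the full 7 days. A termination visit held some days after last dose would shorten that loss.

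Stronger readings are not supported:
- A reader might infer that withdrawn subjects get no safety follow-up. Protocol 6.4, 9.3.3, 9.3.4 and 9.5 show otherwise.
- A reader might infer a bias between the doses and placebo. The documents give no expected dropout by arm and no number of AE-related dropouts, so no direction or size can be stated.
- A reader might infer a threat to the primary result. The Week 13 efficacy analysis, power and alpha do not depend on this contact.

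**What to change.** In Protocol 10.10 and in footnote e (Protocol 16.1 and SAP Table 2), add a safety contact 7 ± 3 days after last dose for every dosed subject who stops early and has not withdrawn consent to contact. It may be a telephone call or a clinic visit and need cover only AEs and concomitant medication. Move final disposition to that contact, or record it after a documented failed attempt. An early termination visit held at least 4 days after last dose, that is, within or after the same window, may serve as the contact.

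The cost is a few lines of wording and about 15 short contacts on the plan's allowance (26 to 38 if dropout were 10% to 15%, an assumption), fewer where contact is refused or the termination visit already qualifies. Sample size and efficacy analyses do not change.
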